1 STUDY SYNOPSIS

Protocol Number:	LT5001-101
Title:	Clinical Pharmacology of LT5001 Drug Product in Hemodialysis Patients with Uremic Pruritus to Assess the Safety, Local Tolerance and Pharmacokinetics.
Sponsor:	Lumosa Therapeutics Co, Ltd
Study Phase:	1 (Part A) and 2 (Part B)
Condition:	Hemodialysis patients with moderate-to-severe pruritus
Background:	Uremic pruritus (UP) is a common and distressing complication of end-stage renal disease (ESRD). A global cross-sectional study of 18,000 hemodialysis patients reported a 42% prevalence of moderate or extreme UP, which was strongly associated with sleep disturbance, depression, impaired quality of life, and mortality. Despite high prevalence and life-altering comorbidities, UP remains lack of effective treatment. Treatments currently used for uremic pruritus such as antihistamines, steroids, emollients, and phototherapy (UVB) have not been investigated rigorously, and no drugs have been approved for this indication by the FDA.
Rationale:	[REDACTED] [REDACTED] [REDACTED] [REDACTED] This study is to evaluate the safety, local tolerance and pharmacokinetics of LT5001 drug product in patients with uremic pruritus.
Objectives:	Part A: To investigate the safety, local tolerance and pharmacokinetics of 4-week, multiple dermal applications of LT5001 drug product to the hemodialysis patients with uremic pruritus. Part B: To investigate the safety, and efficacy of 8-week, multiple dermal applications of LT5001 drug product to the hemodialysis patients with uremic pruritus.

Endpoints:	
Part A:
 
Primary Endpoints
 
• Nature and severity of adverse events (AEs) and number of patients with AEs 
Secondary Endpoints
 
• [REDACTED]• [REDACTED].• Change in mean Worst Itching Intensity from baseline to the end of Week 4 using NRS.• Reduction of itch intensity as assessed by the proportion of patients reduced NRS from baseline (≥ 2 points, ≥ 3 points, or ≥ 4 points) with respect to the weekly mean of the daily 24-hour Worst Itching Intensity NRS score from baseline to the end of Week 4.• Improvement in itch-related quality of life as assessed by the change from baseline in 5-D Itch Scale score at the end of Week 4.• Improvement in itch-related quality of life as assessed by the change from baseline in total Skindex-10 Scale score at the end of Week 4. 
Part B:
 
Primary Endpoints
 
• Change from baseline to end of Week 8 in mean Worst Itching Intensity using NRS. 
Secondary Endpoints
 
• Reduction of itch intensity as assessed by the proportion of patients reduced NRS from baseline with respect to the weekly mean of the daily 24-hour Worst Itching Intensity NRS score from baseline to end of Week 8.• Improvement in itch-related quality of life as assessed by the change from baseline in 5-D Itch Scale score to the end of Week 8.• Improvement in itch-related quality of life as assessed by the change from baseline in total Skindex-10 Scale score at the end of Week 8.• Nature and severity of adverse events (AEs) and number of patients with AEs.
-------------------	---

Subject Population	Inclusion Criteria
	
1. Male or female 20 to 75 years of age, inclusive, at the time of signing informed consent.2. Patient must have been receiving in-center hemodialysis for \geq 3 months and currently on a schedule of 3 times per week.3. Patient must have had at least 2 urea reduction ratio (URR) measurements \geq 65%, at least 2 single-pool Kt/V measurements \geq 1.2, or 1 single-pool Kt/V measurement \geq 1.2 and 1 URR measurement \geq 65% on different dialysis days within the last 3 month period prior to randomization.4. Body weight \geq 40 kg (not to exceed 115 kg) and BMI \geq 18.0 and \leq 31.0 kg/m² at screening (after hemodialysis).5. History of pruritus $>$ 4 weeks of duration6. Females with childbearing potential (defined as women \leq 50 years of age with a history of amenorrhea for $<$12 months prior to study entry) must agree to use effective methods of contraception from screening through the last dose of study drug.7. Males who are sexually active and whose partners are females of childbearing potential must agree to use condoms from screening through 90 days, whichever is longer, after administration of the last dose of study drug, and their partners must be willing to use a highly effective method of contraception from screening through 90 days after administration of the last dose of study drug.8. Males must agree to not donate sperm from screening through 90 days, whichever is longer, after administration of the last dose of study drug.9. Patient must have completed at least 6 days of Worst Itching Intensity NRS worksheets in the 7-day Diary run-in period and have a mean Worst Itching Intensity NRS score $>$ 4 prior to randomization.10. Patients must be able to complete questionnaires, understand the study procedures, and communicate effectively with the study personnel.
	Exclusion Criteria 
1. [REDACTED]2. History of major surgery or trauma within 12 weeks of screening in the judgement of the investigator, or surgery planned during the study.3. [REDACTED]

	
[REDACTED]
 
[REDACTED]
 
4. Has had a significant alteration in dialysis regimen within 2 weeks of the Screening Visit or anticipated to be receiving nocturnal dialysis, home hemodialysis treatment, or kidney transplant during the study.
 
5. Has any known history of allergic reaction to opioids.
 
6. History of latest positive serology test for HBV (HBsAg) or HCV (anti-HCV) within 1 year prior randomization consistent with current infection. Confirmatory tests will be allowed at the discretion of the investigator to rule out false positives.
 
7. Has any known history of HIV.
 
8. Positive pregnancy test or is lactating.
 
9. Has required peritoneal dialysis.
 
10. Alanine aminotransferase and/or aspartate aminotransferase concentration $> 2 \times$ the ULN, or total bilirubin $> 1.8 \times$ ULN, or hemoglobin concentration $< 9 \text{ g/dL}$ at the Screening Visit.
 
11. Has taken other investigational drugs or participated in any clinical study within 30 days or 5 half-lives (if known) of the investigational drug's PK, PD, or biological activity (if known), whichever is longer, prior to first dose of study drug in this study or is currently participating in another clinical study.
 
12. Has received a vaccination within 3 days prior to administration of the first dose of study drug.
 
13. Has pruritus probably or definitely attributed to a cause other than renal disease or its complications such as atopic dermatitis, chronic urticarial, or hepatic pruritus caused by chronic liver disease.
 
14. Presence of skin infection (as defined by the investigator) on the area to be treated.
 
15. Any other condition or prior therapy that, in the investigator's opinion, would make the patient unsuitable for the study, or unable or unwilling to comply with the study procedures
 
16. Involved in the planning or conduct of this study.
 
17. Unwilling or unlikely to comply with the requirements of the study.

--	---

Study Design:	
The study contains two parts: part A will assess the safety, tolerability and PK with 4-week treatment, part B will assess safety and efficacy for 8-week treatment. Both parts will apply investigational drug in hemodialysis patients with moderate to severe of uremic pruritus.
 
Part A:
 
This study will be a randomized, double-blind, placebo-controlled trial to enroll 18 hemodialysis patients (LT5001: Placebo =2:1) with moderate to severe pruritus between the ages of 20 to 75 years old. The study will assess safety, tolerability and the pharmacokinetic profile of LT5001 drug product when applied to skin for 4 weeks with uremic pruritus.
 
After provision of written informed consent, each subject will be evaluated for study eligibility during the screening period, which is within 28 days prior to receiving the study drug (Day 1). During this period, patients need to daily record the worst itch NRS in the patient diary for 7 days (diary run-in). At least 6 of 7 daily Worst Itching Intensity NRS worksheet must be completed and mean NRS score > 4 to qualify. At screening, physical examination of the skin will be conducted as a full-body skin assessment, which will serve as subject's baseline skin condition. Patient's baseline skin condition will be used as reference for comparison in the application site examination from Visit 2 to 8 in Part A. After signing the informed consent, patients may continue but sustain the dosing regimen of all previous antipruritic prescription medication including oral antihistamine agents and/or corticosteroid during the study. However, gabapentin, pregabalin, topical antihistamine/ corticosteroid agents, OTC antihistamine/ corticosteroid agents for anti-pruritus treatment is prohibited throughout the study.
 
Eligible patients will be randomized into LT5001 drug product or placebo treatment groups with 2:1 ratio. [REDACTED] [REDACTED] [REDACTED]
 
Patient will be instructed to directly apply the study drug to the itch area. A fingertip unit of study drug is recommended to treat an area of skin twice the size of an adult palm.
 
In the first 7 days of study treatment, patient will also need undergo a 7-day repeated open application tests (7-day ROAT). A 0.5 fingertip unit of the study drug is recommended to apply to a 5x5 cm² fixed pre-marked zone without any skin lesions near the antecubital fossa twice daily in the morning and evening for 7 days. If skin lesions occurred on the antecubital fossa, accept to choose the volar forearm or ventral inner arm without skin lesion under the judgment of investigator to perform ROAT (avoid the area depicted in the Drug administration section).

----------------------	---

	
Patients will need to daily record the itch condition in the patient diary by themselves including the daily 24-hour worst itch NRS, application time/ site of the study drug, time and intensity of the itch between the morning and evening dose and return the diary at every visit. Patient need to return the study drug and the actual dosing in each patient will be determined by subtract the weight of each returned study drug subtract from the initial weight (T_0).
 
Clinical laboratory tests will be obtained at Day 1, 15, 29. Blood sample for pharmacokinetics will be collected at pre-dose, 48, 120, 168, 336, 504, and 672 hrs post dosing. Subjects will return for a follow-up visit to complete safety evaluations for approximately 35 days after study drug administration.
 
Interim analysis and DSMB:
 
After Part A completion, the interim analysis will plan to be done. DSMB will review interim analysis and give comments on safety or any medical concern to determine whether the study continued or not. Also, DSMB will give comments for LT5001 drug product daily dose and regimen.
 
Part B:
 
This part of study will recruit 90 hemodialysis patients (LT5001: Placebo=1:1) with moderate to severe pruritus. The study will assess safety, and efficacy of LT5001 drug product when applied to skin for 8 weeks with uremic pruritus.
 
Eligible patients will be randomized into LT5001 drug product and placebo treatment groups with 1:1 ratio. [REDACTED] The daily dose and recommended regimen may be adjusted based on DSMB recommendation.
 
Patients will need to daily record the itch condition in the patient diary by themselves including the daily 24-hour worst itch NRS, application site of the study drug, time and intensity of the itch between the morning and evening dose and return the diary at every visit. They will visit at Day 1, 8, 15, 22, 29, 36, 43, 50, and 57 after drug administration.
 
If a subject is withdrawn from the treatment period of the study for reasons not associated with safety considerations, additional subjects may be enrolled if additional data are necessary to establish safety and tolerability.

Estimated Study Duration:	
Part A:
 
Approximately 6 weeks, includes 1 weeks of screening (Diary Run-in), 4 weeks of treatment and 1 week follow up.
 
Part B:

	Approximately 9 weeks, includes 1 weeks of screening (Diary Run-in), 8 weeks of treatment.
Blood Sampling Schedule	
Pharmacokinetic Assessments
 
Blood Pharmacokinetic Assessments
 
[REDACTED]
 
[REDACTED]
 
[REDACTED]
 
[REDACTED]
 
[REDACTED] . [REDACTED]
 
[REDACTED]
 
[REDACTED]
 
 • Pre-dose, 48, 120, 168, 336, 504, and 672 hrs post dosing
Safety Assessments:	The safety and tolerability of LT5001 drug product will be assessed via the following: 
 • Adverse events • Vital signs (temperature, respiratory rate, systolic and diastolic blood pressure, and pulse rate) • Clinical laboratory tests • Physical examination • Application site examination (dermatitis, pruritus, paresthesia, erythema, dryness, vesicles, irritation, papules, burning)
Test Drug	LT5001 drug product

[figure not shown]
Drug Administration	
Topical administration
 
The study medication will be applied directly to the itching area as instructed by the study staff.
 
Avoid apply LT5001 drug product around the eyes, mouth, nose, mucous membrane, genital, anal region, vascular access for hemodialysis and its surrounding region (1 cm in both sides). Do not apply the study medication on to the vesicles, open wound, or on the area of erythema, rash, swelling, paresthesia, pain, desquamation, discoloration.

Sample Size:	
Part A: Approximately 20 subjects will be screened to achieve 18 subjects enrolled (LT5001: Placebo=12:6).
 
Part B: Approximately 100 subjects will be screened to achieve 90 subjects enrolled (LT5001: Placebo=45:45).

Statistical Methods:	
Safety Analyses
 
All safety analyses will be performed on the safety analysis set (SAS).
 
Adverse events will be coded by System Organ Class and Preferred Term using the current version of MedDRA. Incidences of treatment-emergent AEs (TEAEs), ie, events that started after exposure to study drug or worsened in severity after dosing, will be presented by dose group. Incidences of TEAEs will also be presented by maximum severity and relationship to study medication.
 
Safety data will be summarized through appropriate data tabulations, standard descriptive statistics, and graphical presentations. For each continuous laboratory parameter, results will be categorized as low, normal, or high based on the laboratory normal ranges. Frequencies and percentages will be presented by dose group for subjects who had a shift to low and for subjects who had a shift to high from baseline to any post-dosing assessment.
 
The association of AEs, clinical laboratory tests, vital sign measurements with the actual dosing of study drug or systemic exposure of LT5001 drug product may also be explored. If appropriate, statistical modeling will be performed to further characterize the associations mentioned above. All out-of-range and clinically significant laboratory results will be identified in subject data listings. The number and percentage of subjects in each dose group with normal and abnormal physical examination results will be presented for evaluations at baseline and final visit.
 
For each body system, changes in the subjects' findings from baseline to final visit (no change, normal to abnormal, or abnormal to normal) will be tabulated for each dose group.
 
Pharmacokinetics Analyses

	
Pharmacokinetics Parameters
 
From the concentration-time data, the following blood PK parameters will be determined, as data permit:
 
C_{trough} Lowest observed blood concentration prior to next application
 
All calculations for PK parameters will be based on actual dosing and sampling times recorded during the study. Considering the actual dose received by each patient may vary, the PK parameter will be adjusted by dividing to the actual dose of each patient
 
Adjusted PK parameter= C_{trough} / Actual Dose
 
In addition, the original blood PK parameter (without dose adjustment) versus time will also be analyzed. Blood concentrations that are below the limit of quantification (BLQ) prior to the first measurable concentration will be set to zero, BLQ values that are between measurable concentrations will be set to missing, and BLQ values that occur at the end of the profile (after the last quantifiable concentration) will be set to missing.
 
Pharmacokinetic parameters will be listed by subject and treatment using the SAS, and summarized by treatment using the using the pharmacokinetic analysis set (PKAS) and the following summary statistics: n, arithmetic mean, standard deviation (SD), CV%, minimum, median, and maximum. Geometric mean and geometric CV% will also be presented for all PK parameters.
 
Scatter plots of individual adjusted PK parameters (C_{trough} / Actual Dose) and non-adjusted PK parameters (C_{trough}) versus time for LT5001 drug product will be produced on log-log scales using the PKAS.

--	---

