5 STUDY DESIGN

5.1 Study Design and Overview

This study contains 2 parts. Both study parts will include hemodialysis patients with moderate to severe UP. Part A will assess the safety, tolerability, and PK of LT5001 drug product with 4-week of daily BID topical dosing. Part B will assess safety and efficacy with 8-week of daily topical dosing. The maximum daily dose and recommended regimen for Part B will depend on DSMB comments.

Part A:

Part A will be a randomized, double-blind, and placebo-controlled. It will enroll 18 patients between 20 to 75 years of age, inclusive.

After providing written informed consent, each patient will be evaluated for study eligibility within 28 days of Day 1. During this period, patient need to daily record the worst itch NRS in the patient diary for 7 days (diary run-in). At least 6 of 7 daily Worst Itching Intensity NRS worksheet must be completed and mean NRS score > 4 to qualify. At screening, physical examination of the skin will be conducted as a full-body skin assessment, which will serve as subject's baseline skin condition. Photographs of the treatment area may be considered under the investigator's judgment (optional). Patient's baseline skin condition will be used as reference for comparison in the application site examination from Visit 2 to 8 in Part A. After signing the informed consent, patients may continue previous antipruritic therapy throughout the study prescribed by the physician (unless specified in the prohibited medication [Section 7.7.3](#)). The dosing regimen of the previous antipruritic therapy cannot be changed. Gabapentin, pregabalin, topical antihistamine/ corticosteroid agents, OTC antihistamine/ corticosteroid agents are prohibited throughout the study. Eligible patients will be randomized into 2 groups (LT5001 drug product and Placebo) at a ratio of 2:1. [REDACTED]

[REDACTED]
Topical dosing will occur for 4 weeks, consisting of 56 total doses throughout the treatment period. Patient will be instructed to directly apply the study drug to the itch area. A fingertip unit of study drug is recommended to treat an area of skin twice the size of an adult palm.

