After providing written informed consent, each patient will be evaluated for study eligibility during screening (within 28 days of Day 1). During this period, patient need to daily record the worst itch NRS in the patient diary for 7 days (diary run-in). At least 6 of 7 daily Worst Itching Intensity NRS worksheet must be completed and mean NRS score > 4 to qualify. At screening, physical examination of the skin will be conducted as a full-body skin assessment, which will serve as subject's baseline skin condition. Photographs of the treatment area may be considered under the investigator's judgment (optional). Patient's baseline skin condition will be used as reference for comparison in the application site examination from Visit 2 to 9 in Part B.

After signing the informed consent, patients may continue all previous antipruritic therapy prescribed by the physician throughout the study (unless specified in the prohibited medication [Section 7.7.3](#)). The dosing regimen of the previous antipruritic therapy cannot be changed. Gabapentin, pregabalin, topical antihistamine/ corticosteroid agents, OTC antihistamine/ corticosteroid agents are prohibited throughout the study. Eligible patients will be randomized into 2 groups (LT5001 drug product and Placebo) at a ratio of 1:1. Topical dosing will occur for 8 weeks. [REDACTED]

[REDACTED] Topical dosing will occur for 8 weeks. Patients will need to daily assess the

itch condition at a fixed period by themselves and record in the patient diary including the daily 24-hour worst itch NRS, application site/ time of the study drug, time and intensity of the itch between the morning and evening dose, and return the diary every visit.

Patients will visit the CRU for dosing on Day 1 and procedures including clinical laboratory test sampling, physical examinations, vital sign assessments, and itch assessment (Skindex-10 and 5D-itch scale), and application site assessments (dermatitis, pruritus, paresthesia, erythema, dryness, vesicles, irritation, papules, burning) by ICDRG scale according to Table 8.2, AEs, and concomitant medications and procedures will be performed according to [Table 2.2](#). Application site evaluation will be conducted in each visit (Visit 2 to 9) in Part B. Photographs of the application site may be considered under the investigator's judgment (optional). Baseline skin condition performed at screening will be used as reference for comparison.

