6.2 Exclusion Criteria

Patients will not be eligible for study participation if they meet any of the exclusion criteria, or will be discontinued at the discretion of the investigator in consultation with the medical monitor if they develop any of the exclusion criteria during the study.

- [REDACTED]
- [REDACTED]
- 2. History of major surgery or trauma within 12 weeks of screening in the judgement of the investigator, or surgery planned during the study.
- 3. [REDACTED]
- [REDACTED]
- [REDACTED]
- 4. Has had a significant alteration in dialysis regimen within 2 weeks of the Screening Visit or anticipated to be receiving nocturnal dialysis, home hemodialysis treatment, or kidney transplant during the study.
- 5. Has any known history of allergic reaction to opioids.
- 6. History of a latest positive serology test for HBV (HBsAg) or HCV (anti-HCV) within 1 year prior randomization consistent with current infection. Confirmatory tests will be allowed at the discretion of the investigator to rule out false positives.
- 7. Has any known history of HIV.
- 8. Positive pregnancy test or is lactating.
- 9. Has required peritoneal dialysis.
- 10. Alanine aminotransferase and/or aspartate aminotransferase concentration $> 2 \times$ the ULN, or total bilirubin $> 1.8 \times$ ULN, or hemoglobin concentration $< 9 \text{ g/dL}$ at the Screening Visit.
- 11. Has taken other investigational drugs or participated in any clinical study within 30 days or 5 half-lives (if known) of the investigational drug's PK, PD, or biological activity (if known), whichever is longer, prior to first dose of study drug in this study or is currently participating in another clinical study.
- 12. Has received a vaccination within 3 days prior to administration of the first dose of study drug.
- 13. Has pruritus probably or definitely attributed to a cause other than renal disease or its complications such as atopic dermatitis, chronic urticarial, or hepatic pruritus caused by chronic liver disease.
- 14. Presence of skin infection (as defined by the investigator) on the area to be treated.

15. Any other condition or prior therapy that, in the investigator's opinion, would make the patient unsuitable for the study, or unable or unwilling to comply with the study procedures
16. Involved in the planning or conduct of this study.
17. Unwilling or unlikely to comply with the requirements of the study.

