8.8.3 Other Tests

The following test history will be reviewed or performed:

- History of latest serology test (ie, HBsAg, HCV antibody, and any confirmatory tests performed at the discretion of the investigator)
- History of HIV
- Serum or urine β -hCG test (females only)

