9.5 Pregnancy

Pregnancies will be captured if they occur in female patients from the time the patient is first exposed to the study drug until 30 days after the last exposure or the last study visit, whichever occurs later. Pregnancies in the sexual partners of male patients will be captured from the time the patient is first exposed to the study drug until 90 days after last exposure to the study drug.

Female patients must be instructed to discontinue all study drugs and inform the study investigator immediately if they become pregnant during the study.

The investigator must report any pregnancy to the Sponsor or designee within 1 business day of becoming aware of the pregnancy per pregnancy reporting procedures described in the SRM.

The patient must be immediately discontinued from further treatment with study drug. An uncomplicated pregnancy will not be considered an AE or SAE; however, all pregnancies will be followed through birth and 3 months post delivery.

Any congenital abnormalities in the offspring of a patient who received study drug will be reported as an SAE. The outcome of any pregnancy and the presence or absence of any congenital abnormality will be recorded in the source documentation and reported to the Sponsor.

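### Criterion 6 caps childbearing potential at age 50 although women may enrol to 75, so a woman over 50 who has menstruated in the last 12 months has no contraception requirement while dosed

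*Protocol*

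**What the plan says.** Criterion 1 sets the age range for both sexes: "Male or female 20 to 75 years of age, inclusive, at the time of signing informed consent". Criterion 6 then requires effective contraception, from screening to the last dose, of females with childbearing potential. It defines them as women at or below "50 years of age with a history of amenorrhea for" less than 12 months. The synopsis and Section 6.1 carry the same definition.

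The other readable provisions on pregnancy in female patients have no age limit:

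- Section 8.8.3 lists a serum or urine β-"hCG test (females only").
- Exclusion 8 in Section 6.2 reads "Positive pregnancy test or is lactating". The opening of Section 6.2 allows a patient who comes to meet an exclusion during the study to be discontinued, at the investigator's discretion after consulting the medical monitor.
- Section 9.5 states: "Female patients must be instructed to discontinue all study drugs and inform the study investigator immediately if they become pregnant during the study".

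In Part A dosing lasts 4 weeks. For Part B, Section 5.1 says "Topical dosing will occur for 8 weeks".

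**The concern.** The definition uses age as well as menstrual status, and the age limit sits 25 years below the upper limit for enrolment. Take two women with the same menstrual history on the same drug and schedule, one aged 50 and the other 51. The first must use contraception and the second need not. The readable text gives no reason for drawing the line there.

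What is at stake is an unintended pregnancy exposed to an investigational drug. The gap falls in the dosing period, when exposure is intended. No claim is made that LT5001 harms an embryo; the documents do not allow that to be judged either way. This is a matter of participant safety wording and has no bearing on the efficacy or safety analyses.

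**Working it through.** No arithmetic settles this point. The check is to apply criterion 6 to each type of woman whom criterion 1 admits, and then to look for any other rule that would require contraception.

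**Step 1. Apply the definition.** Both conditions must be met for the requirement to apply.

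| Age at consent | Amenorrhea before entry | Meets criterion 6 definition? | Contraception required? |
|---|---|---|---|
| 20 to 50 | less than 12 months | yes | yes |
| 20 to 50 | 12 months or more | no | no |
| 51 to 75 | 12 months or more | no | no |
| 51 to 75 | less than 12 months | no, fails on age alone | no |

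The last row is the gap. These women pass criterion 1 and fail the definition only because of age.

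**Step 2. Look for another source of the requirement.**

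- Protocol Section 7.7.4 (other restrictions) covers only taking part in other trials and donating blood or plasma.
- Protocol Section 8.8.3 tests females of any age. A test detects pregnancy.
- Exclusion 8 bars entry after a positive test and, through the opening of Section 6.2, can lead to discontinuation on study. Both act after conception.
- Exclusion 15 lets the investigator refuse a patient judged unsuitable. It is discretionary and does not mention contraception.
- Protocol Section 9.5 has a patient who becomes pregnant stop drug and report it. This also acts after conception.
- SAP Section 11.4 places the pregnancy test at screening and adds no rule on contraception.

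No readable text supplies the missing requirement.

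**Step 3. Check what cannot be seen.** Protocol Section 8.8.2 refers to Table 8.1 for the timing of the β-hCG test. That table and the visit schedules (Tables 2.1 and 2.2) are not shown, and exclusions 1 and 3 are redacted. Repeat pregnancy testing during treatment therefore cannot be ruled out. If it exists, it shortens the time to detection, but it does not prevent conception or change the definition in criterion 6.

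**The case against.** The strongest reply is that an age limit is a sponsor's choice, applied identically in both places, and that the gap may contain no patients at all. Women over 50 who still menstruate are likely to be few among hemodialysis patients, and the documents give no count. Those who do enrol are tested for pregnancy, can be discontinued under exclusion 8, can be refused under exclusion 15 and must stop drug if they become pregnant. Some will be on placebo.

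Much of this stands. It limits the weight of the point and shows that such women are not without protection. It does not answer the point, because every safeguard listed either follows conception or is discretionary. Nor is redacted nonclinical material likely to explain an age line: if it showed that contraception was unnecessary, criterion 6 would not require it of a woman of 50.

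Three stronger readings might be inferred, and the documents support none of them.

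- A reader might take the width of the uncovered age band, or the number of scheduled doses, as the size of the problem. The band counts calendar ages, most of them well past the usual age of menopause. The doses only describe the regimen, which for Part B may change on DSMB advice. Neither shows how many women are affected.
- A reader might carry the age cap into criterion 7, which begins "Males who are sexually active and whose partners are females of childbearing potential must agree to use condoms". The definition is a parenthesis inside criterion 6 and is tied to study entry, so it describes participants. Criterion 7 neither repeats it nor refers to it, and whether it applies to partners is uncertain.
- A reader might call it an error that a treated woman's requirement ends at the last dose while the partner of a male patient has a further 90 days. The nonclinical and pharmacokinetic basis is redacted, and the 30-day window in Section 9.5 is a reporting rule, so the documents do not show that the difference is wrong.

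**Conclusion.** The point holds as a narrow gap in eligibility wording. An eligible woman over 50 who has menstruated in the last 12 months has no contraception requirement during 4 or 8 weeks of dosing, and nothing readable in the protocol or SAP gives her one. The group is assumed to be small; its size cannot be derived from the documents and could be nil. The conclusion rests on reading the two parts of the definition as joint conditions, which is their plain sense, and on the redacted exclusions and unseen tables containing no contraception rule. It should be corrected because the correction is cheap and the requirement is one that the protocol already imposes on women just below the cap. It is not a reason to doubt the trial's results.

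**What to change.** In criterion 6, in both the synopsis and Section 6.1, delete the age-50 cap and define childbearing potential by status. Suggested wording: any woman who is not surgically sterile and not postmenopausal, where postmenopausal means at least 12 months of amenorrhea before study entry without another medical cause.

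The last phrase is needed. A test of 12 months of amenorrhea alone would still exempt a younger woman whose amenorrhea has some other cause, as the present text does.

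The cost is an amendment to two passages and any matching consent text, with no added visits or tests. The burden is a contraception commitment for the few women newly covered: those over 50 who have menstruated in the last 12 months, and any whose amenorrhea is not menopausal.
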